8.1.5 Missing Not At Random for MMRM

In addition, an imputation sensitivity analysis will test the assumption of MAR that is made by the MMRM analysis foreseen for the analysis of the cumulative OCS exposure (mg/kg) from baseline to Week 36 and from baseline to Week 16.

For this purpose, a model that assumes MNAR will be used, whereby assumptions for the missing data “stress test” the MAR assumptions of the primary analysis, by positing outcomes that, while clinically plausible, are likely to be worse for the benralizumab group than the outcomes assumed by MAR. A plausible stress test could assume that the outcome for the benralizumab treatment is somewhat worse than would be predicted by MMRM from the study data. Such a stress test would appropriately disadvantage the estimate of treatment effect, compared to the estimate of the main analysis.

The proposed MNAR sensitivity analysis assumes that the trajectory after the intercurrent event from the benralizumab group, regardless of the type of event, can be modelled by that of placebo participants. This assumption will tend to result in smaller estimates of difference between the treatment groups, compared to those under the MAR assumption, and as such constitutes a reasonable stress test of the MAR assumption. Note that this approach constitutes a pattern mixture model as defined by [Molenberghs 2007](#). The patterns here are defined by the time of the intercurrent event, with the imputed values for both treatment groups modelled by observed outcomes from the placebo group only. Specifically, for a participant with missing observations after visit t , imputed value for the change from baseline at visit $t+n$ will be based on a model estimated from all in the control group who have an outcome observed at visit $t+n$ conditioning on that participant’s outcomes up to and including visit t . Then, the overall estimate of treatment effect is obtained by using Rubin’s rules [Rubin 1987] to combine the imputed outcomes. Note that in this analysis, placebo missing are imputed assuming MAR and here follows the pattern of observed placebo observations, while missing observations for the benralizumab group are assumed MNAR. This strategy for imputation is commonly referred to as the Copy-Reference approach. In summary, the pattern mixture models will be implemented by multiple imputation via the following steps;

Step 1: Non-monotone missing data (usually relatively infrequent) will be imputed using the MCMC statement of SAS PROC MI under the MAR assumption. The following variables will be included in the imputation model: treatment, baseline disease severity, time of BP diagnosis and cumulative OCS exposures from baseline to Week 36 by 4-weekly intervals. Note: Dummy variables will be used for treatment, baseline disease severity and time of BP diagnosis. This will create a monotone missing pattern in the dataset within each treatment group. This step will create 1000 imputed datasets.

Step 2: Then the values for each pattern will be imputed via the sequential regression method, using SAS PROC MI statement MONOTONE REG. The imputation model will be estimated

from the observed data in the placebo group and it will be used to impute missing observations in both treatment groups using the MNAR statement of SAS PROC MI. The following variables will be included in the imputation model: baseline disease severity, time of BP diagnosis and cumulative OCS exposures from baseline to Week 36 by 4-weekly intervals.

Step 3: The imputed data from Step 1 and Step 2, along with observed data will be analyzed using the same MMRM model as for the main analysis. The estimates from multiple imputed datasets will be combined using Rubin's combination rules for statistical inference (using PROC MI ANALYZE).

The seed used will be 88281 for both steps 1 and 2.

8.1.6 On-treatment analyses

In addition to the primary and sensitivity analyses described previously, two alternative estimands may be estimated for primary and key secondary endpoints, using only the data from participants while on initial randomised treatment:

- Primary on-treatment estimand: This will be estimated using the primary method but including only data from participants whilst being on initial randomized treatment. Participants who drop from randomized treatment are imputed as non-responders.
- Efficacy estimand: This will be estimated using the MAR method above described but including only data from participants whilst being on initial randomized treatment.
- Effectiveness estimand: Assumed loss of effect post discontinuation of benralizumab: This will be estimated using the DRMI controlled imputation approaches including only data from participants whilst on treatment.

Therefore, the primary analyses and sensitivity analyses will be repeated including only data from participants whilst being on initial randomised treatment, i.e., excluding data once participants discontinue from randomised treatment (including on-treatment period to IPD visit or last contact if the participant is lost to follow-up).

A summary of reasons for participants withdrawing from the benralizumab treatment group and the corresponding treatment group used to calculate the imputed response probability under MAR and DRMI are given in Table 10. As for participants who withdraw from the study, a review of each participant who discontinued randomised treatment will be carried out prior to unblinding the study where the default assumptions for DRMI as described in Table 9 may be changed. Again, a list of these participants and the assumptions made under DRMI will be documented prior to unblinding of the study.

Table 10 Summary of reasons for participants withdrawing from the benralizumab treatment and the corresponding treatment group used to calculate the imputation response rate under MAR and DRMI

Reason for withdrawal	MAR	DRMI
Adverse Event	Benralizumab	Placebo
Development of study-specific discontinuation criteria	Benralizumab	Placebo
Death	Benralizumab	Placebo
Severe non-compliance to protocol	Benralizumab	Placebo
Participant lost to follow up	Benralizumab	Benralizumab
Participant decision	Benralizumab	Based on review prior to study unblinding
Other	Benralizumab	Based on review prior to study unblinding

Note all participants on response rate in the placebo treatment group are imputed using the placebo treatment group rate

Using on treatment data is easier to interpret as it is not impacted by any subsequent pattern of alternative treatments once participants discontinue from randomised treatment. Sensitivity analyses under DRMI allow for alternative assumptions to be made based on reasons for discontinuation.

8.1.7 Treatment policy estimand

A pure treatment policy strategy may also be applied in another sensitivity analysis performed for primary and key secondary endpoints without considering restricted medications/ OCS dose increase as a rescue therapy, as applicable based on the endpoint, as intercurrent events.

8.1.8 Overall summary of sensitivity analyses to account for missing data

A summary of the different sensitivity analyses for the primary endpoint to be carried out under different estimands and assumptions are described in Table 11.

Sensitivity analyses and multiple imputation analyses might be performed on key secondary outputs if deemed appropriate. Full details of the sensitivity analyses will be finalized as an update to the Statistical Analyses Plan (SAP) before primary database lock.

Table 11 Summary of the analyses to be carried out under different estimands and assumptions

Assumption	On-treatment + post-discontinuation of randomised treatment				On-treatment		
	No missing data	MAR		MNAR	No missing data	MAR	MNAR
Estimand	Primary	Treatment policy	MAR MI	DRMI	On-treatment	MAR MI	DRMI
Responder/Non-responder status for imputation in benralizumab treatment group ^a	Participants who receive restricted medications and participants who withdraw from the study are imputed as non-responders	Participants who withdraw from the study are imputed as non-responders.	Benralizumab rate for all reasons for withdrawal assumed to be on benralizumab	Placebo rate for AEs, death, development of study specified reasons to stop active treatments and severe non-compliance to protocol assumed to be on, otherwise benralizumab or based on review prior to study unblinding	Participants who receive restricted medications and participants who withdraw from the study or the randomized treatment are imputed as non-responders	Benralizumab rate for all reasons for withdrawal assumed to be on benralizumab	Placebo rate for AEs, death, development of study specified reasons to stop active treatments and severe non-compliance to protocol assumed to be on, otherwise benralizumab or based on review prior to study unblinding
Default definition for p_{ij} based on formula (2) ^b			Formula (2) for all treatment groups. $j = B$ or P .	Formula (2) using $j = P$ for reasons above. Otherwise, $j = B$ or P (same as MAR)		Formula (2) for all treatment groups. $j = B$ or P .	Formula (2) using $j = P$ for reasons above. Otherwise, $j = B$ or P (same as MAR)

^a All participants in the placebo treatment group are imputed using the placebo treatment group rate (i.e., $j = P$)

^b Note can be over written by review prior to study unblinding

B – Benralizumab; P – Placebo

Forest plots will be used to show the primary analysis results along with the missing data sensitivity and alternative estimand analysis results.

It is noted that if the primary analysis is statistically significant, it is not necessarily expected that all sensitivity analyses will also give statistically significant results. If the results of the sensitivity analyses provide reasonably similar estimates of the treatment effect to the primary analysis, this will be interpreted as providing assurance that neither the lost information nor the mechanisms which cause the data to be missing have an important effect on primary analysis conclusions. Based on these outputs and the drug's mechanism of action, the plausibility of the assumptions we make about missing data in the different analyses will be considered and described in the clinical study report.

8.2 Analysis plan for immunogenicity data

Serum samples for ADA assessments will be conducted utilizing a tiered approach (screen, confirm, titre) and ADA data will be collected at scheduled visits shown in the CSP. ADA result from each sample will be reported as either positive or negative. If the sample is positive, the ADA titre will be reported as well.

In general, participants with a missing baseline ADA assessment will be assumed to be ADA negative at baseline as a conservative approach to ensure that all participants are included in all analyses. If a positive ADA titre result is reported as ≤ 50 , then the titre will be imputed as 50 for titre summaries. ADA results from samples collected post-dose instead of pre-dose on an IP administration day are considered unreliable and should be excluded from all derivations.

For each participant, the following ADA responses will be evaluated over the entire on-study period through EOT:

Participants who are ADA positive at any time during the study, including baseline and/or post-baseline (also generally referred to as ADA positive). The proportion of ADA positive participants in a population is known as ADA prevalence.

Participants who are ADA negative at all assessments, including baseline and postbaseline (also generally referred to as ADA negative).

Participants who are ADA positive at baseline only.

Participants who are ADA positive at baseline and at least one post-baseline assessment.

Treatment-emergent ADA positive (referred to as ADA incidence). A positive post-baseline result and either of the following statements holds:

Baseline is ADA negative and at least one post-baseline assessment is ADA positive. This is called treatment-induced ADA positive.

Baseline is ADA positive, and the baseline titre is boosted by greater than the variability of the assay (ie, ≥ 4 -fold increase) at ≥ 1 post-baseline timepoint. This is called treatment-boosted ADA positive.

Participants who are persistently ADA positive, which is defined as ADA negative at baseline and having at least 2 post-baseline ADA positive measurements with ≥ 16 weeks between first and last positive, or an ADA positive result at the last available post baseline assessment.

Participants who are transiently ADA positive, defined as ADA negative at baseline and at least one post- baseline ADA positive measurement and not fulfilling the conditions for persistently positive.

Participants who are ADA positive with maximum titre > median of maximum titres. The median of maximum titres will be calculated based on the maximum titre of each ADA positive participant within each treatment group (including both baseline and post-baseline measurements).

The responses above will be summarized as counts and percentages by treatment group. The maximum ADA titre over the on-study period will also be summarized for participants in each of the ADA positive response categories listed above. The maximum titre will be derived based on all available ADA titres reported for each participant, including any unscheduled assessments.

ADA response (positive or negative) and titre will be summarized at baseline and at all scheduled post-baseline visits by treatment group. In the event a participant has more than one result within a given visit window, the maximum ADA titre will be used in the by-visit summary. In addition, the ADA response will be presented cumulatively. The cumulative ADA response is positive for a specific visit if a positive ADA result is detected at any time point up to and including the specific visit. If all ADA result are negative up to the specific visit, then the cumulative ADA response is negative for that visit. A summary of the number and percentage of participants who are ADA positive at a post-baseline assessment for the first time by visit will also be presented. A line plot of the proportion of participants who are ADA positive at each visit will be provided.

The proportion of participants with ADA persistently positive response will be summarized by visit and treatment group.

Key participant information will be listed for participants with positive ADA results, including ADA status, titer, benralizumab serum concentration, and eosinophil level.

All analyses will be conducted on the safety analysis set by treatment group unless otherwise specified. All ADA results will be listed.

8.2.1 ADA and efficacy

Since ADA will not be tested in the placebo group, no statistical comparisons of benralizumab versus placebo by ADA status (positive/negative) are planned. The effects of ADA on the primary and key secondary endpoints calculated through EOT will be evaluated through summary statistics by ADA status (treatment-emergent ADA positive, ADA negative), if enough data are available.

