- k Complete physical examination includes an assessment of the following: height and weight, general appearance, skin, head and neck (including eyes, ears, nose, mouth, and throat), lymph nodes, abdomen, musculoskeletal (including spine and extremities), cardiovascular, respiratory, and neurological systems.
- l Brief physical examination includes assessment of the following: weight, general appearance, skin, abdomen, cardiovascular, and respiratory system. For the brief physical examination, only information on whether the assessment was performed or not is to be recorded. Weight measurements will be performed in light clothing and without shoes and will be recorded in kilograms.
- m Testing to be conducted at local laboratory, confirmation testing to be conducted by a central laboratory.
- n A positive urine pregnancy test result must be confirmed with a serum pregnancy test.
- o Confirmatory local testing is required for those who do not have a confirmed BP diagnosis.
- p An unscheduled hematology and clinical chemistry should be performed if the visit is for relapse.
- q If not conducted in the previous 3 months.
- r Samples will be taken only at one time point, ie, at the visit when disease control has been achieved.
- s Samples will be taken at an unscheduled visit if the visit is for relapse.
- t Blood biomarkers will be collected only at one of the time points between Visits 4 and 6; ie, only at the visit that disease control has been achieved and before steroid taper is commenced.
- u Skin biopsies will be taken from peri-lesional skin for histopathology and CCI [REDACTED] research.
- v For participants without a confirmed diagnosis, no biopsy for CCI [REDACTED] is collected. In these participants, the biopsy will be for inclusion criteria confirmation at the local lab and immunohistochemistry for exploratory research.
- w Benralizumab administration only; for participants who continue the study in the open-label extension.

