## BP Relapse

In the event of a suspected BP relapse (see [Table 6](#) for definition), the participant should attend an unscheduled visit. A BPDAI evaluation will be conducted at the time of the relapse, or as soon as possible afterwards.

Investigators will be required to record details pertaining to each relapse event in the eCRF from baseline (Visit 2) until IPD visit/end of treatment and follow-up visit. Details should include the BPDAI activity and pruritus score and the required intervention(s), eg, OCS dose increase, the OCS dose at the time of relapse, addition of immunosuppressive therapy or requirement for hospitalization. Participants who require the addition of OCS after taper or an increase in the dose of OCS will be defined as having a relapse.

The management of participants who relapse will be according to standard of care. See [Section 6.5.1](#) for further details. The participant's relapse is managed with the addition of OCS and tapering should be recommended as soon as the relapse has been appropriately controlled as per current guidelines ([Feliciani et al 2015](#)). In case of a relapse during steroid tapering, the OCS dose may be increased to the previous dosage that symptoms were controlled. For recurrent relapses the OCS dosing regimen and tapering schedule will be at the Investigator's discretion. If the participant requires therapy other than OCS (eg, immunosuppressants), the study treatment may need to be discontinued but this should be discussed with the study physician prior to decision making. In the event that discontinuation of IP is required, the participant will still be asked to continue with the study assessments until the end of the double-blind period at Week 36. For relapse during OLE, the use of topical and/or oral corticosteroids and the schedule of taper will be at the discretion of the Investigator; however, it is recommended to follow the protocol taper schedule. The goal of therapy will be to taper off steroids to benralizumab monotherapy as soon as clinically indicated. In the event that the Investigator will need to control relapse with an immunosuppressant in the OLE, the participant will be withdrawn from the study and will not receive further benralizumab therapy. Participants may additionally be asked to allow future contact to provide follow-up clinical details regarding their health and information on disease state.

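### Relapse-triggered ADA samples appear to count towards ADA status, which can tilt the descriptive ADA-by-efficacy summary against ADA-positive participants

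*SAP*

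**What the plan says.** **Sampling.** The ADA/nAb row of the Schedule of Activities (Protocol 1.3, Table 2) carries footnote s in the unscheduled-visit column: "Samples will be taken at an unscheduled visit if the visit is for relapse". For a suspected relapse, the BP Relapse text in Protocol 8.1.1.1 says "the participant should attend an unscheduled visit".

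**Status.** SAP 8.2 defines the ADA-positive category as "Participants who are ADA positive at any time during the study, including baseline and/or post-baseline". The treatment-induced part of treatment-emergent ADA needs only this: "Baseline is ADA negative and at least one post-baseline assessment is ADA positive". The ADA-negative category is "Participants who are ADA negative at all assessments, including baseline and postbaseline". The one exclusion rule in the section covers samples taken after dosing on a dosing day.

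**Unscheduled results.** For titre, SAP 8.2 is explicit: "The maximum titre will be derived based on all available ADA titres reported for each participant, including any unscheduled assessments". For status it gives no such sentence, and it opens by saying that "ADA data will be collected at scheduled visits shown in the CSP".

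**Use.** SAP 8.2.1 says: "The effects of ADA on the primary and key secondary endpoints calculated through EOT will be evaluated through summary statistics by ADA status". The groups are treatment-emergent ADA-positive and ADA-negative participants, and the summary is made if there are enough data. Placebo participants are not tested for ADA, so no comparison with placebo is planned.

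**The concern.** A relapse-free participant cannot have an unscheduled ADA sample, while a participant who attends an unscheduled relapse visit gets at least one more. Under an any-positive rule, more samples mean more chances of a positive, and a participant must be negative on every sample to be called negative. The chance of being classified ADA positive then depends partly on relapse. Freedom from relapse to Week 36 is the first key secondary endpoint in the 8.2.1 table. Relapse is treated with OCS, so it also feeds into cumulative OCS exposure and can make remission off OCS less likely.

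At stake is how the table is read. Protocol 2.3 lists reduced efficacy as a potential risk of ADA, and SAP 8.2.1 describes the table as evaluating effects of ADA. A gap produced by sampling frequency could be reported as loss of efficacy.

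**Working it through.** The plan states no figure on this point, so there is none to reproduce. The check asks how large a gap appears when ADA and relapse are truly unrelated.

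**Inputs**
- Benralizumab arm: about 50 (SAP 1.3).
- k, scheduled post-baseline ADA samples in the double-blind period: 3 or 4. This is an assumption. The extracted table is broken; it is read here as disease control plus Weeks 16, 24 and 36.
- m, relapse-visit samples: 1 or 2 (assumption).
- q, chance that one sample is positive: 2% to 10% (assumption).
- r, proportion relapsing: 30% to 70% (assumption).

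**Case 1: independent samples**

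P0 = P(ADA positive | no relapse) = 1 − (1 − q)^k.
P1 = P(ADA positive | relapse) = 1 − (1 − q)^(k+m).

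With k = 4, m = 1, q = 5%, r = 50%:
- P0 = 1 − 0.95^4 = 18.5%; P1 = 1 − 0.95^5 = 22.6%.
- Relapse-free among ADA positive = (1 − r)P0 / [(1 − r)P0 + rP1] = 0.1855 / (0.1855 + 0.2262) = 45.1%.
- Relapse-free among ADA negative = 0.8145 / (0.8145 + 0.7738) = 51.3%.
- Spurious gap: 6.2 points. Expected ADA positive: 50 × (18.5% + 22.6%)/2 ≈ 10.

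Over the whole grid the gap runs from 4.7 points (q = 2%, k = 4, m = 1, r = 70%) to 15.4 points (q = 10%, k = 3, m = 2, r = 50%), always against ADA-positive participants.

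**Case 2: correlated samples**

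This case was simulated with 400,000 participants per setting, samples at Weeks 6, 16, 24 and 36, half relapsing at a uniform time between Weeks 8 and 36, one relapse sample, and ADA onset at 0.5% or 1% per week independent of relapse.

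| Mean ADA duration | Relapse-free, ADA+ vs ADA− (0.5%/week) | Relapse-free, ADA+ vs ADA− (1%/week) | Gap (points) |
|---|---|---|---|
| 4 weeks | 47.7% vs 50.1% | 48.0% vs 50.3% | 2.4, 2.3 |
| 8 weeks | 48.4% vs 50.1% | 48.5% vs 50.3% | 1.7, 1.8 |
| 16 weeks | 49.1% vs 50.1% | 49.2% vs 50.2% | 1.0, 1.0 |
| Persistent | 50.4% vs 50.1% | 50.0% vs 50.1% | about 0 |

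The persistent result follows by reasoning too: ADA present at a relapse visit is still present at Week 36, so the extra sample changes nobody's status.

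**Precision of the table**

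With 10 ADA positive and 40 ADA negative, the 95% half-width for 45.1% against 51.3% is 1.96 × √(0.451×0.549/10 + 0.513×0.487/40) = 1.96 × 0.176 ≈ 35 points.

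**Scheduled-only status**

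With equal follow-up, relapsers and non-relapsers have the same chance of a positive (18.5% for k = 4, 14.3% for k = 3, at q = 5%), so the expected gap is 0.

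**The case against.** The strongest reply is that the SAP never says relapse samples enter ADA status. It names unscheduled results only for titre and describes collection at scheduled visits. This stands as a statement about the text, but it does not remove the point. The collection sentence does not fit footnote s or the titre rule, it sets no rule for deriving status, and the definitions cover every assessment without excluding these. At the least, the SAP leaves the rule unclear.

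Several offsets also stand:
- Withdrawal counts as not relapse-free (SAP 3.3.1), and early withdrawers give fewer samples, which pulls the other way.
- OCS rescue, restricted medication and missing data also count as not relapse-free, and none of them in itself triggers an ADA sample.
- A relapse first seen at a scheduled visit adds no unscheduled sample.
- A participant who relapses, is rescued and tapers again can still be a primary responder (SAP 3.2).

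A reader might infer that ADA-positive participants must look worse whatever the truth. The documents do not support that. SAP 8.2 has a persistent-positive category, and with persistent ADA the gap is about 0. For the same reason, the increase in the chance of a positive under independence (18.5% to 22.6% in the example) is not the expected size.

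A reader might also infer that nothing could reveal the artefact. The lack of ADA testing on placebo removes one check, but SAP 8.2 lists all ADA results, and SAP 8.2.3 and 8.2.4 set ADA status against eosinophils and drug concentration.

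Finally, relapse samples may be the best placed to detect ADA-related loss of response, and Amendment 3 kept them because they are needed at relapse. That is a sound argument against discarding them. It is no argument against also showing the table without them.

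**Conclusion.** The concern holds in a limited form. As written, SAP 8.2 lets samples that exist only because of relapse count towards ADA status, and SAP 8.2.1 then summarises relapse-free status and related endpoints by it. The direction of this effect is against ADA-positive participants. Its size is unknown: about 0 with persistent ADA, about 1 to 2.5 points with transient episodes, and 5 to 15 points only with independent repeat samples. All of these assume no true link between ADA and relapse and complete follow-up.

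Any of these gaps is small beside a half-width of about 35 points. The table is descriptive, confined to the benralizumab arm and conditional on enough data. It would be wrong to infer any threat to the main results, because ADA status plays no part in the primary analysis or the testing hierarchy (SAP 4.1.1). This is a cheap improvement to how a secondary summary is read.

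**What to change.** In SAP 8.2.1:
1. State that relapse-triggered unscheduled samples count in the all-sample ADA status.
2. Present the efficacy summary also by ADA status derived from fixed-week scheduled samples only. Name the weeks, because the disease-control sample is itself timed by outcome. Select by nominal visit rather than analysis window, so that a relapse sample falling inside a window does not re-enter.
3. Base any statement about an effect of ADA on efficacy on agreement of the two versions.

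Keep the all-sample definition for prevalence, incidence, titre and listings.

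The cost is one extra flag and one extra table from data already collected. A positive seen only at a relapse visit does not count in the scheduled-only version, though it stays in the all-sample version and the listings. Unequal follow-up from withdrawal remains in both.
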